## **Safety Endpoints**

### MONOCULAR BSCVA

Mean monocular BSCVA will be reported by test and control groups with the mean difference between postoperative and preoperative BSCVA evaluated using a two-sided, 90% confidence interval (CI). The null hypothesis is that the mean difference (postoperative minus preoperative) in logMAR BSCVA is greater than or equal to 0.1 logMAR. The alternative hypothesis is that the mean difference in BSCVA is less than 0.1 logMAR.

$H_0: \mu_{\text{diff}} \geq 0.1$

$H_1: \mu_{\text{diff}} < 0.1$

where

$\mu_{\text{diff}}$  = the mean difference in logMAR BSCVA between postoperative and preoperative eyes (postoperative minus preoperative).

The success criterion is achieved if the upper limit of the 90% CI of the differences in mean logMAR BSCVA for postoperative compared to preoperative eyes is < 0.1 logMAR for both test and control groups.

Clinical significance is achieved if the mean postoperative BSCVA is no more than one line worse than preoperative BSCVA for both test and control groups.

#### INDUCED MANIFEST REFRACTIVE ASTIGMATISM

The frequency and proportion of eyes with induced manifest refractive astigmatism will be reported at each periodic study visit. The rate of eyes with induced manifest refractive astigmatism of greater than 2.00 diopters will be summarized.

#### SERIOUS AND DEVICE RELATED ADVERSE EVENTS

The number and proportion of eyes with serious and device-related adverse events (non-flap related) will be summarized.

### **20.3 ADDITIONAL ENDPOINTS**

The frequency, proportion and 95% confidence intervals of eyes with achieved MRSE within 0.50 D and 1.00 D of intended will be summarized over time. The intended MRSE is defined as “ – Preop MRSE”. The achieved MRSE is defined as “Postop MRSE - Preop MRSE”.

Refractive stability will be evaluated for a consistent cohort (i.e., eyes with data at all periodic study visits). At the point of refractive stability, at least 95% of the eyes in the consistent cohort should have a change  $\leq 1.00$  D of MRSE between refractions performed at 1 month and 3 months after surgery or any two refractions performed at least 3 months apart. The mean change (paired differences) in MRSE between pairs of successive refractions will be calculated. The 95% confidence intervals of the mean changes should include zero.

The depth of focus curve data will be presented graphically and test and control groups will be compared by descriptive analysis. The mean and standard deviation of iDesign aberrometry measurements (HOA) and keratometry (mean and K cylinder) will be reported over time. Manifest cylinder will be analyzed as both non-vector and vector variables (Eydelman, et al, 2006). The frequency and proportion of eyes with

complications and slit-lamp findings, including corneal clarity, will also be reported over time. Other visual acuity endpoints (such as UCDVA, UCIVA, UCNVA and low contrast BSCVA) will also be reported by test versus control group with the mean difference between groups also determined. Results for visual symptoms from the PRVSQ for PRK/LASIK will be analyzed to compare differences between the test and control groups. The frequency and proportion of eyes with reported ocular visual symptoms (non-directed) will be presented. A listing of all serious and/or device-related adverse events will also be provided. Additionally, non-refractive retreatment procedures will be tabulated and summarized.

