## **6. STUDY OBJECTIVES AND ENDPOINTS**

The purpose of this study is to determine whether wavefront-guided LASIK correction of myopic refractive errors with PresbyT-LASIK treatments mitigate the effects of presbyopia by increasing the depth of focus compared to iDesign CustomVue treatments. All study endpoints will be evaluated at 6 months.

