## **6.3 OTHER ENDPOINTS**

- UCDVA and BSCVA, monocular and binocular
- UCIVA and UCNVA, monocular and binocular
- DCIVA and DCNVA, binocular
- Low contrast BSCVA (10%), monocular
- Mesopic DCNVA, monocular
- Depth of focus, monocular
- iDesign aberrometry measurements (higher order aberrations)
- Pupil size, photopic and mesopic, distance and near
- Manifest refraction
- Keratometry (auto or manual)
- Anterior segment evaluation (biomicroscopic slit-lamp exam) for determination of medical findings
- Visual symptoms via the patient reported outcomes (PRO) instrument Patient Reported Visual Symptom Questionnaire (PRVSQ) for PRK LASIK
- Ocular/visual symptoms (from non-directed responses obtained from the open-ended question “Are you having any difficulties with your eyes or vision?”).

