### PERIODIC POSTOPERATIVE EXAMINATION PROCEDURES

Periodic examinations will be conducted at 1, 3, 6, and 9 months after treatment. In the event that extended follow-up is not needed, the follow-up period may be reduced.

Note: Subjects are not to wear contact lenses postoperatively until after completion of this study. Wearing contact lenses may potentially cause corneal edema or topography

changes that may influence the visual acuity results. During the study, if correction is required, spectacles should be prescribed.

The following data shall be assessed and recorded for both eyes during the periodic examinations, although not all are required at all periodic visits (see also **Appendix A**). General descriptions and requirements of the various tests are provided in **Appendix C**.

- Ocular and systemic medical history and concomitant medications
- PRVSQ Questionnaire (1, 3, 6, and 9 month visit)
- iDesign System Measurement (refraction, aberrometry, topography, keratometry, pupillometry)
- UCDVA, photopic, monocular
- UCDVA, photopic, binocular
- Manifest Refraction (logMAR)
- BSCVA, photopic, monocular, distance (logMAR)
  - At 3 months or later, if there is a loss of 2 or more lines of BSCVA ( $\geq 10$  letters) compared to the preoperative visit, a rigid contact lens over refraction should be performed to estimate the best possible corrected visual acuity. If a rigid contact lens over refraction is not medically advisable, then a pin-hole acuity should be obtained
- BSCVA, photopic, binocular, distance (logMAR) (3, 6, and 9 month visit)
- BSCVA, photopic, monocular, distance low contrast, 10%, (logMAR) (3, 6, and 9 month visit)
- DCNVA, mesopic, monocular at 40 cm (3, 6, and 9 month visit)
- Pupil size
  - Mesopic, distance and near (3 month visit)
  - Photopic, distance and near (3 month visit)
- DCIVA, photopic, monocular (3, 6, and 9 month visit)
- DCIVA, photopic, binocular (3, 6, and 9 month visit)
- DCNVA, photopic, monocular (3, 6, and 9 month visit)
- DCNVA, photopic, binocular (3, 6, and 9 month visit)
- UCIVA, photopic, monocular (3, 6, and 9 month visit)
- UCIVA, photopic, binocular (3, 6, and 9 month visit)
- UCNVA, photopic, monocular (3, 6, and 9 month visit)
- UCNVA, photopic, binocular (3, 6, and 9 month visit)
- Defocus curve testing (3, 6, and 9 month visit)
- Anterior Segment Examination

- Pachymetry (6 month exam)
- Auto or Manual Keratometry
- Corneal Topography
- Cycloplegic Refraction (6 month exam)

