## APPENDIX J INSTRUCTIONS FOR DEFOCUS CURVE TESTING USING THE M&S SYSTEM

All defocus curve testing is to be performed using the M & S Technologies CTS-1000 Smart System in logMAR format (100% contrast) at a distance of 4.0 meters and calibrated to a photopic luminance of 85 cd/m^2 (range 80-110 cd/m^2 is acceptable).

The M&S system background luminance is set to 85 cd/m^2 (range of 80 – 110 cd/m^2 is acceptable). Room lighting is to be set at a level lower than the illumination from the laptop. Ambient lighting should be mesopic (30-50 lux) to maximize pupil size. No surface (including reflective surfaces) within the subject's field of vision should exceed the laptop in luminance.

Subjects should be reminded prior to testing that squinting is not allowed. During defocus curve testing, trial frames will be used to allow observation by the testing technician to ensure the subject is not squinting. If squinting is observed, the subject is to be reminded by the testing technician not to squint.

This test is to be done on all subjects.

Monocular Defocus Curve Testing: Starting with the subject's distance correction in place, begin testing by occluding the left eye and defocusing the image by +2.00 D over the manifest distance correction in the right eye. Subjects should be instructed to start with the smallest line where they can read all of the letters. If they miss any letters, go up a line until they are able to read all the letters on a line, then continue to read each subsequently smaller line. The subject should be encouraged to read as many letters possible, even if they have to guess. Testing may be stopped when it is evident that no further readings can be made. Record the total number of letters read correctly on the chart. This will be displayed on the laptop screen along with the logMAR and Snellen acuity. Then reduce the amount of defocus in the right eye by -0.50 D, to +1.50 D, and repeat the acuity test, recording the visual acuity LogMAR value. Continue to change the defocus in -0.50 D increments in the right eye, repeating the test and documenting the visual acuity LogMAR value at each level of defocus. Continue to change the defocus to -3.00 D over the subject's distance correction.

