2.3 DATA CONVENTIONS

Descriptive statistics will typically include sample size (N), mean, standard deviation (SD), median, minimum (Min.), and maximum (Max.) as appropriate for continuous variables. For categorical data, the frequency and proportion will be computed.

Unless otherwise indicated, alpha will be set to 0.05 for two-sided statistical testing.

For visual acuity data, letter scores will be converted to LogMAR values prior to analysis. In addition, if the test distance used is not the standard test distance for the chart, then visual acuity data will be adjusted for the actual test distance used. Appendix II provides formulas for LogMAR conversion and distance adjustment.

For refractive data, all values will be converted to minus cylinder format and sphere will be adjusted for optical infinity. Formulas used for refractive data conversions are included in Appendix III.

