3.6 ADDITIONAL ENDPOINTS

Summary statistics (mean, standard deviation, median, minimum and maximum) will be reported over time for MRSE.

The frequency, proportion and 95% confidence intervals of eyes with achieved MRSE within 0.50 D and 1.00 D of intended will be summarized over time. The intended MRSE is defined as " – Preop MRSE". The achieved MRSE is defined as "Postop MRSE - Preop MRSE".

Refractive stability will be evaluated for a consistent cohort (i.e., eyes with data at all periodic study visits). At the point of refractive stability, at least 95% of the eyes in the consistent cohort should have a change ≤1.00 D of MRSE between refractions performed at 1 month and 3 months after surgery or any two refractions performed at least 3 months apart. The mean change (paired differences) in MRSE between pairs of successive refractions will be calculated. The 95% confidence intervals of the mean changes should include zero.

The depth of focus curve data will be presented graphically with mean visual acuity on the vertical axis and defocus points on the horizontal axis for test and control groups. The descriptive statistics of defocus for test and control groups will be reported and compared.

Other visual acuity endpoints (such as UCDVA, UCIVA, UCNVA, DCIVA, DCNVA and low contrast BSCVA) will also be reported by test versus control group with the mean difference between groups also determined.

The mean and standard deviation of iDesign aberrometry measurements (HOA) and keratometry (mean and K cylinder) will be reported over time between test and control gorups.

Manifest cylinder will be analyzed as both non-vector and vector variables (Eydelman, et al, 2006). Non-vector analysis includes the descriptive statistics (mean, SD, minimum and maximum) of MRC over time between test and control groups and the accuracy of MRC will also be summarized over time. Vector analysis summary will be reported by test and control group. The mean and standard deviation of intended refractive change (|IRC|), surgically induced refractive change (|SIRC|), error vector (|EV|), correction ratio (CR) and error ratio (ER) will be presented by preoperative MRC categories (>0.50 D to $\leq 1.00 \text{ D}$, >1.00 D to \leq to 2.00 D, >2.00 D to \leq to 3.00 D, >3.00 D to \leq 4.00 D).

Summary statistics (mean, standard deviation, median, minimum and maximum) will be reported over time for pupil size between test and control groups.

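### The study asks whether depth of focus increases, but the defocus curves get only a plot and group descriptive statistics, with no paired difference or interval

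*Protocol*

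**What the plan says.** Protocol section 6 gives the purpose as determining whether the test treatment will "mitigate the effects of presbyopia by increasing the depth of focus compared to iDesign CustomVue treatments". Section 6.3 lists "Depth of focus, monocular" among the other endpoints, without a definition, unit or acuity threshold.

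Appendix J starts testing at +2.00 D over the distance correction and moves in 0.50 D steps: "Continue to change the defocus to -3.00 D". Section 10.6 schedules this at 3, 6 and 9 months, under a general instruction: "The following data shall be assessed and recorded for both eyes during the periodic examinations". No preoperative curve is scheduled.

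For analysis, Protocol 20.3 says: "The depth of focus curve data will be presented graphically and test and control groups will be compared by descriptive analysis". SAP 3.6 has the curves "presented graphically with mean visual acuity on the vertical axis and defocus points on the horizontal axis for test and control groups", and continues: "The descriptive statistics of defocus for test and control groups will be reported and compared". SAP 2.3 describes such statistics as typically N, mean, SD, median, minimum and maximum. SAP Appendix I has no defocus row.

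**The concern.** The defocus curve is the only measurement in the study that traces acuity across a range of focus, which is what the purpose refers to. The plan never turns it into a value per eye and never takes the difference between a subject's two eyes.

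Each subject is their own control, so the relevant uncertainty is that of the within-subject difference. A plot of two group means, with an SD for each group, does not contain it. A reader of the final report would see two curves but could not tell how precisely the gap between them is known.

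There is also a pre-specification issue. With no summary fixed beforehand, any acuity threshold or dioptric range quoted later could have been chosen after the curves were seen.

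**Working it through.** **Inputs.** 34 subjects, a 0.7-line difference, an SD of 1.4 lines and two-sided alpha 0.05 (Protocol 20.6, SAP 4). Dominant eye control, non-dominant eye test (Protocol 4). Test distances 67 cm and 40 cm (Protocol 20.2). Defocus range and step (Protocol Appendix J). The documents give no SD for any defocus quantity and no between-eye correlation, so those are assumed ranges below.

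**1. The plan's own figure.** Paired t-test, df = 33, noncentrality = (0.7/1.4) × √34 = 2.92. Exact power is 80.8%, and 34 is the smallest n that reaches 80%. The stated figure of over 80% reproduces. It concerns intermediate acuity; the documents state no precision for depth of focus.

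**2. What is collected and what is tested.** Levels: (2.00 + 3.00)/0.50 + 1 = 11 per curve. The two paired tests sit at 1/0.67 = 1.49 D and 1/0.40 = 2.50 D.

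**3. Why group statistics are not enough.** With complete pairs, the difference between group means equals the mean paired difference, so the plot shows the right acuity difference at each level. Its SD is another matter. If both eyes have SD s and between-eye correlation r, then SD of the difference = s√(2(1 − r)). The 95% half-width with 34 pairs is t(0.975, 33)/√34 = 0.349 times that SD.

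| Assumed r | SD of difference | 95% half-width |
|---|---|---|
| 0 | 1.41 s | 0.49 s |
| 0.5 | 1.00 s | 0.35 s |
| 0.8 | 0.63 s | 0.22 s |

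The same reported group SDs are compatible with half-widths that differ by a factor of √(1/0.2) = 2.24 over this range of r. The missing correlation cannot be recovered from the planned output.

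Nor can depth of focus in dioptres be read safely off the mean curve. The point where the mean curve crosses a threshold is not in general the mean of the eyes' own crossing points.

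**4. Precision if paired differences were reported.** At a single defocus level, assuming the 1.4-line planning SD also applied there, the half-width is 0.349 × 1.4 = 0.49 line (0.049 logMAR). For a per-eye depth of focus in dioptres:

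| Assumed SD of paired difference (D) | 95% half-width (D) | Difference detectable with 80% power, about 0.5 SD (D) |
|---|---|---|
| 0.25 | 0.09 | 0.13 |
| 0.50 | 0.17 | 0.25 |
| 0.75 | 0.26 | 0.38 |
| 1.00 | 0.35 | 0.50 |
| 1.50 | 0.52 | 0.75 |

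**5. Are there two curves per subject?** Protocol 10.6 says periodic data are recorded for both eyes. Appendix J says the test is done on all subjects, but writes out the sequence for the right eye with the left occluded, and no left-eye sequence follows. If only right eyes were tested, the comparison would be between different subjects. With an assumed even split of 17 and 17, the half-width is t(0.975, 32) × √(2/17) = 0.70 times the per-eye SD. That is twice the paired value at r = 0.5.

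**The case against.** The strongest reply is that the objective already has inference. The clinical hypothesis makes it operational as better DCIVA and DCNVA. Both are measured through the distance correction, both are tested as paired differences, and both carry clinical thresholds (1 and 1.5 lines). Depth of focus is an other endpoint in a feasibility study, and no success criterion depends on it. That stands: leaving the curves descriptive is a limitation, not an error in the primary analysis. A reader might infer that the trial cannot say whether focus improved at all. The documents do not support that, because it can say so at two vergences.

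A reader might also infer that no estimates are planned. That goes too far as well. Group means at each level are estimates, and with N and SD each group's own standard error follows. Only the paired standard error is absent.

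Protocol 20.4 says t-tests will generally be used for continuous variables, and 20.3 and SAP 3.6 promise a mean difference for an open-ended list of other acuity endpoints. These soften the point but do not close it. The specific sentence on defocus data says descriptive, neither clause gives these data a paired interval, and no depth-of-focus variable is defined to test.

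The missing Appendix I row proves little. Pupil size, UCIVA, UCNVA and low-contrast BSCVA also have no row, although SAP 3.6 commits to reporting them. The more telling comparison is that Appendix I does plan a paired difference with a 95% CI for higher-order aberrations, though it does not say whether the pairing is between eyes or visits.

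**Conclusion.** The point holds as a cheap improvement to a supportive analysis. The quantity named in the purpose gets a plot and group statistics, and the plan gives no direct estimate with valid uncertainty of the change across the defocus range. DCIVA and DCNVA cover two vergences within it.

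The size depends on an SD that the documents do not give. The half-width is 0.349 times the SD of the paired difference, or 0.09 to 0.52 D over the assumed range of 0.25 to 1.50 D. This rests on 34 complete pairs at 6 months and on curves from both eyes, which Protocol 10.6 supports but Appendix J does not spell out.

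An area under the logMAR curve should not be read as depth of focus. It is average acuity over a chosen range, in which a loss at 0.00 D can offset a gain at -2.00 D. With no preoperative curve, only the between-eye contrast is available, not a change from baseline.

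**What to change.** In Protocol 20.3 and SAP 3.6, keep the plot and add the following at 6 months, labelled supportive with no alpha allocated:

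- The paired mean logMAR difference with a 95% CI at each of the 11 defocus levels, as control minus test to match the sign in Protocol 20.2. State that the intervals are unadjusted.
- One per-eye summary fixed before analysis, with its paired mean difference and 95% CI. One option is the trapezoid area from 0.00 to -2.50 D divided by 2.50 D, described as average acuity over that range; it uses 6 of the 11 levels. The other is the dioptric range at a stated acuity threshold, with a rule for interpolating between levels and for eyes still meeting the threshold at -3.00 D. The second is the one that expresses depth of focus in dioptres.

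Add the table to SAP Appendix I. Reconcile Protocol 10.6 with Appendix J so that it is clear both eyes are tested.

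The cost is a few lines of text and one table. If both eyes are already meant to be tested, no new visits, measurements or subjects are needed. The downside is that the summary and its range or threshold must be chosen and defended in advance.

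Suggested SAP wording: *For each defocus level at 6 months, the mean within-subject difference in logMAR acuity (control minus test) will be reported with a 95% confidence interval, together with the same contrast for the pre-specified per-eye summary. These analyses are supportive.*

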#### **20.4 VISUAL ACUITY CONVENTIONS AND GENERAL STATISTICS**

Visual acuity data will be converted to LogMAR values prior to analysis and adjusted for the test distance. Descriptive statistics will typically include sample size (N), mean, standard deviation (SD), median, minimum (Min) and maximum (Max) as appropriate for continuous variables. For continuous variables, statistical tests (e.g., t-test) assuming normality will generally be used. For categorical data, the frequency and proportion will be reported and Fisher's exact test or Chi-square test will generally be applied. For ordinal categorical data, the frequency and proportion will be reported with the Wilcoxon Rank-Sum test generally used.

#### **20.5 PERIODIC REPORTS**

Periodic analyses of data from all eyes completing the 3-month and 6-month visits to evaluate UCDVA, MRSE, BSCVA, DCIVA, DCNVA and safety outcomes including biomicroscopic findings and adverse events will be conducted.

#### **20.6 SAMPLE SIZE CALCULATIONS**

The sample size determination is based on intermediate visual acuity. There is over 80% power to detect a 0.7 line or greater difference in mean visual acuity between the test and control eyes with 34 subjects. This assumes a two-sided paired t-test with an alpha of 0.05 and standard deviation of 1.4 lines.

## APPENDIX A SUMMARY OF PROCEDURES REQUIRED AT EACH VISIT

Examination	Preop Days -120 to -21 	CL Disp Weeks -3 	CL F/U Weeks -2 	Op Day 0	1 Day Days 1-2	1 Wk Days 5-9	1 Mo Weeks 3-5	3 Mo Weeks 10-14	6 Mo Weeks 21-26	9 Mo Weeks 35-43	Unsched 
Informed consent	X										
Ocular and systemic medical history and concomitant medications	X			X	X	X	X	X	X	X	
Inclusion/Exclusion criteria	X										
PRO questionnaire - PRVSQ	X						X	X	X	X	X 
iDesign System Measurement of refraction, aberrometry, topography, keratometry, pupilometry	X					X	X	X	X	X	X (after 1 week)
UCDVA - photopic, monocular, distance (logMAR)	X				X	X	X	X	X	X	X (after 1 week)
UCDVA - photopic, binocular, distance (logMAR)								X	X	X	
Manifest refraction (logMAR)	X					X	X	X	X	X	X
BSCVA - photopic, monocular, distance (logMAR)	X					X	X	X 	X 	X 	X 
BSCVA - photopic, binocular, distance (logMAR)								X	X	X	
BSCVA - photopic, monocular, distance low contrast (10%) (logMAR)	X							X	X	X	
DCNVA - mesopic, monocular at 40 cm (logMAR)								X	X	X	
Pupil size, mesopic, distance & near								X			
Pupil size, photopic, distance & near								X			
Minimum add power	X										
DCIVA - photopic, monocular at 67 cm (logMAR)	X							X	X	X	
DCIVA - photopic, binocular at 67 cm (logMAR)	X							X	X	X	
DCNVA - photopic, monocular at 40 cm (logMAR)	X							X	X	X	
DCNVA - photopic, binocular at 40 cm (logMAR)	X							X	X	X	
UCIVA - photopic, monocular at 67 cm (logMAR)								X	X	X	
UCIVA - photopic, binocular at 67 cm (logMAR)								X	X	X	
UCNVA - photopic, monocular at 40 cm (logMAR)								X	X	X	
UCNVA - photopic, binocular at 40 cm (logMAR)								X	X	X	
Defocus curve testing – photopic, monocular (logMAR)								X	X	X	
Keratometry (auto or manual)	X					X	X	X	X	X	X 
Corneal topography	X						X	X	X	X	X 
Anterior segment exam (biomicroscopic slit-lamp exam  )	X				X	X	X	X	X	X	X
Intraocular pressure (applanation tonometry)	X						X	X	X	X	X 
Pachymetry	X								X		
Cycloplegic refraction	X								X		X 
Dilated fundus exam	X								X		X 
Complications	X	X	X	X	X	X	X	X	X	X	X

Examination	Preop Days -120 to -21 	CL Disp Weeks -3 	CL F/U Weeks -2 	Op Day 0	1 Day Days 1-2	1 Wk Days 5-9	1 Mo Weeks 3-5	3 Mo Weeks 10-14	6 Mo Weeks 21-26	9 Mo Weeks 35-43	Unsched 
Adverse events (Ocular/NonOcular)	X 	X	X	X	X	X	X	X	X	X	X
Device deficiencies/complaints	X			X		X	X	X	X	X	X
Contact lens trial		X	X								
Refractive stability assessment for contact lens wearers				X 							

 All screening assessments must be performed prior to surgery. The screening period is the 120 days before surgery, up to and including the day of surgery.

 The contact lens trial should occur after the preoperative exam at any time during the 120 days before the day of surgery. However, subjects must wear the trial contact lenses for a minimum of 1 week and remove the contact lenses for a minimum of 2 weeks prior to surgery.

 At 3 months or later, if there is a loss of 2 or more lines of BSCVA ( $\geq 10$  letters) compared to the preoperative visit, a rigid contact lens over refraction (or pin hole acuity if rigid contact lens over refraction is medically inadvisable) should be performed to estimate the best possible corrected visual acuity.

 At the investigator's discretion for unscheduled visits based on the reason for the unscheduled visit. Subject seen at an unscheduled visit due to an optical/visual symptom complaint should complete the PRVSQ.

 Adverse event collection begins after informed consent has been obtained.

 On operative day or other visit

**Note:** Patient reported outcome questionnaires are to be administered first, followed by the iDesign measurement before any other ocular examinations. All non-contact procedures (e.g. topography and keratometry) are to be performed before contact assessments (e.g. IOP and pachymetry). Cycloplegic refraction/fundus exam are to be the final procedures.

**Note:** 1 month = 4 weeks, 1 week = 7 days

